**A1. Primary Hypothesis**

Fewer patients assigned to the CLASP intervention will have subsequent suicide attempts compared to those receiving SAFE.

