**A2. Secondary Hypotheses**

When compared to patients receiving SAFE, patients assigned to the CLASP intervention will have: a) fewer re-hospitalizations due to suicide risk, and b) lower severity and chronicity of suicidal ideation.

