#### 3) Tertiary Outcomes

- a. *Treatment Engagement*. Is defined here as the # of participants seeing a mental health professional in the month prior to a given assessment (i.e. 3-, 6-, 9-, or 12-month), as indexed by the Treatment History interview.
- b. *Psychiatric Symptoms*. We will utilize the Global Symptom Index from the BSI to assess overall severity of psychiatric symptoms.
- c. *Psychosocial Functioning*. We will compare CLASP vs. SAFE patients on relevant measures of psychosocial functioning, e.g. the WHO-DAS and SS-B.
- d. *Completed suicide*. Given the relatively low incidence of completed suicide, even in this high risk sample, we do not expect to have sufficient numbers of patients who complete suicide for meaningful analyses. However, since completed suicide is a critical outcome, we will track number of completed suicides, using all possible data sources, including significant other reports, chart reviews, community provider reports and reviews of state and national death registries.

**F3.2 Treatment Outcome Analyses.** Effect sizes between patients receiving the CLASP intervention and those receiving SAFE will be computed for each outcome measure. Specifically, for our primary dependent measure (proportion of patients who make suicide attempts), we will calculate an effect size of the difference in the proportions between CLASP and SAFE groups using an odds ratio and its associated robust confidence interval. Effect size estimates will be adjusted by significant covariates in analyses.

Supplanting this estimate will be an analysis of our graded ordinal measure of outcomes. We will employ Generalized Estimating Equations (GEE; [78]) to estimate the ordinal response at each follow-up assessment. GEE have the advantage of providing developed methods for the flexible handling of missing data under various assumptions [79]. Similar analyses will be conducted to obtain estimates for the CLASP effect on the total number of attempts in each treatment condition, suicidal ideation, completed suicide, re-hospitalization due to suicide, and treatment engagement. For continuous indices we will employ robust estimates of effect size obtained in two-level repeated measures analysis [80].

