#### **F5. Statistical Power**

Statistical power was based upon effect size estimates derived from the CLASP pilot as well as our judgment about how large a difference would represent a clinically significant difference. In our pilot study, for suicide attempts, we found that 3 of 39 (~8%) individuals assigned to CLASP made a suicide attempt compared to 10 of 47 (~21%) randomized to control, yielding an effect size between small and medium ( $d = .38$ ; 95% CI: .31 - .45). Similarly, for psychiatric re-hospitalization, we found that 8 of 39 (~20.5%) individuals assigned to CLASP were re-hospitalized for suicide risk compared to 17 of 47 (~36%) randomized to control, yielding an effect size between small and medium ( $d = .35$ ; 95% CI: .28 - .41). Consequently, we believed that it was important to power the proposed study for effect sizes slightly larger than small ( $\sim d = .25$ ) to provide adequate coverage for the full range of expected effect sizes.

Sample size for effect size and odds ratio comparisons for the primary treatment outcomes was estimated using Fisher's Exact Test using our primary treatment outcome, # of suicide attempts. Assuming the proportions identified in the CLASP pilot,  $\alpha = .05$ , a one-tailed hypothesis test, and our projected sample of 200, our power estimate for this conservative test will be .82. It should also be noted that given the longer follow-up period in the current study, we hypothesize that the difference in

proportions obtained in our pilot study are likely to be higher due to the longer period of risk assessed. Consequently, the proposed study design should have ample power to test our primary hypothesis.

To estimate power for latent growth curve models, we used Zhang & Wang's [81] simulation procedure for SAS 9.1.3. Our simulation assumed five repeated measures assessments (Baseline, 3-, 6-, 9-, and 12-month), a moderate correlation between slopes and intercepts ( $r = .30$ ), a total missing data rate of ~30%, and 2500 simulation replications per sample size. We simulated sample sizes ranging from 50 to 300 in 10 participant intervals for our lower-bound effect size estimate ( $d = .28$ ). The proposed sample of participants ( $N = 200$ ) should be adequate (Power > .80) to detect even our lower-bound effect size for the full sample.

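### F3.2 replaces the powered odds-ratio estimate with an undefined ordinal analysis, and the test that decides the primary hypothesis is not fixed

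*Combined protocol and SAP*

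**What the plan says.** Hypothesis A1 is per patient: "Fewer patients assigned to the CLASP intervention will have subsequent suicide attempts compared to those receiving SAFE". F3.2 follows it, calling the odds ratio the effect size for "our primary dependent measure (proportion of patients who make suicide attempts"), with a robust confidence interval. It adds: "Effect size estimates will be adjusted by significant covariates in analyses". No covariates are listed, and neither the interval's level nor the sidedness of the test is given.

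The following paragraph opens: "Supplanting this estimate will be an analysis of our graded ordinal measure of outcomes". The method is GEE, applied to the response at each follow-up. The document gives no categories, scoring rule, source instrument or deciding time point for this measure.

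F5 sizes the trial for effect-size and odds-ratio comparisons using Fisher's exact test on the pilot proportions, with alpha .05, "a one-tailed hypothesis test, and our projected sample of 200". It concludes that "our power estimate for this conservative test will be .82".

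The labels for the primary outcome vary. F3.1 puts the number of patients with an attempt and the total number of attempts under the one primary heading. F3 refers both to the number of attempts and, more broadly, to suicidal behavior. F5 labels the primary as a count of attempts although its inputs are proportions. F1 plans a Benjamini-type adjustment for the number of tests, but names neither the family of tests nor the test that decides A1.

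**The concern.** There are two gaps, and the first is the more serious.

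1. **A stated rule is wrong as written.** A statistician who followed F3.2 literally would set aside the estimate that A1 asks for and F5 powers. In its place would go an analysis whose outcome has not been defined and whose power is not given.
2. **The test of the proportion is not pinned down.** Correcting the verb still leaves two candidates: the unadjusted one-tailed Fisher test of F5, and the F3.2 odds ratio with covariates that qualify by being significant, which can be known only once data are in hand. Nothing says which result settles A1, or whether an odds-ratio interval is to be read one-sided or two-sided.

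What is at stake is the confirmatory claim. If the deciding analysis is not named before outcomes are compared by arm, it can be chosen after the results are seen, and the power of .82 may not belong to the analysis that is reported.

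**Working it through.** **Consistency of the passages**

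| Section | Primary quantity | Analysis |
|---|---|---|
| A1 | patients with an attempt | none named |
| F3.1 | patients with an attempt, and total attempts | none named |
| F3.2, first paragraph | proportion of patients with an attempt | odds ratio, robust interval, adjusted for significant covariates |
| F3.2, second paragraph | ordinal measure, undefined | GEE at each follow-up |
| F5 | count of attempts by label, proportions by input | one-tailed Fisher, unadjusted |

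A1, the first paragraph of F3.2 and the inputs to F5 agree on the per-patient proportion. The second paragraph of F3.2 is the one that conflicts with them. The only ordinal scale described nearby is the 6-point LIFE rating in F3.1. That is a secondary ideation measure (A2 b: "lower severity and chronicity of suicidal ideation") and nothing links it to this phrase. F3.2 also lists ideation separately among the further analyses.

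**Inputs for power**
- Attempt rates from F5: CLASP 3/39 = .0769; SAFE 10/47 = .2128.
- Arm size: 200 patients in total (F5) and 100 in CLASP (D2), so 100 per arm. Equal allocation is inferred.
- Alpha .05.

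**The plan's own figure.** Let X be the number of CLASP patients with an attempt, Binomial(100, 3/39), and Y the number in SAFE, Binomial(100, 10/47). Power is the sum of P(X = x)P(Y = y) over all tables (x, y) whose one-tailed Fisher p-value is at most .05. Exact enumeration gives **.833**, close to the stated .82. With the rates rounded to .08 and .21 it gives .799. The stated figure is therefore sound for the test it describes.

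**The other readings of the same comparison.** The pilot odds ratio is (3/36)/(10/37) = .308. For each table (x, y), take

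log OR = ln[x(100 − y) / (y(100 − x))]

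SE = √[1/x + 1/(100 − x) + 1/y + 1/(100 − y)]

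with .5 added to every cell of a table that has an empty cell. Without covariates, the robust standard error in a two-group logistic model equals this SE. Count the tables with log OR/SE below −1.645 (one-tailed .05) or with |log OR/SE| above 1.96 (two-sided 95% interval excluding 1), and weight them by the same binomial probabilities.

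| Deciding analysis | Power |
|---|---|
| Fisher, one-tailed (F5) | .833 |
| Odds ratio, unadjusted, one-tailed | .875 |
| Odds ratio, unadjusted, two-sided 95% interval | .783 |
| Fisher, two-tailed | .743 |

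The spread is .875 − .743 = .132, with identical data assumptions throughout. Both one-tailed readings reach .82 and both two-sided readings miss it.

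**What cannot be computed.** The ordinal GEE needs categories, their expected distribution and a deciding time point. Total attempts needs a rate and a dispersion. The adjusted odds ratio needs the covariates and their prognostic strength. The documents give none of these.

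**The case against.** The strongest reply is that the plan is clearer than this makes it sound. The primary measure is largely fixed: A1, the parenthesis in F3.2 and the inputs to F5 all point to the per-patient proportion. F3.2 puts total attempts among its further analyses ("Similar analyses will be conducted to obtain estimates for the CLASP effect on the total number of attempts in each treatment condition"), together with ideation and re-hospitalization. F5 offers Fisher as a conservative way to size odds-ratio comparisons, so the two need not be rivals, and at F5's own sidedness the unadjusted odds ratio does better (.875). Read as supplementing, the disputed sentence displaces nothing.

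Much of this stands. The loose labels in F3, F3.1 and F5 are a lesser point, and a reader who inferred that the primary outcome is wholly open would go too far. But the reply depends on correcting a word that the text does not correct. After that correction the ordinal measure is still undefined, the covariates are still to be found by significance, and the sidedness of the odds ratio is still unstated.

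A reader might also infer that the type I error rate is inflated by some definite amount, because several tests could each count as success. The documents do not support that. F1 plans an adjustment for the number of tests, and a figure that ignored it would mislead. F1's limitation is that it identifies neither the family nor the deciding test. Nor can one say that the ordinal analysis would gain or lose power, since its categories are unknown.

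**Conclusion.** The point holds and should be corrected before outcomes are compared by arm. As written, F3.2 replaces the estimate behind A1 and F5 with an analysis that has no defined outcome and no stated power. A slip of wording is the likely cause, but the sentence is wrong as it stands. In addition, the deciding test of the proportion is not fixed. The stated .82 is right for the one-tailed Fisher test (.833 recomputed), but it does not describe a two-sided reading, where power is .783 for the odds-ratio interval or .743 for Fisher.

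These figures assume the exact pilot rates, 100 analysed patients per arm, no covariates and no missing outcomes. The finding on the text depends on none of these assumptions.

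**What to change.** - In F3.2, change *Supplanting* to *Supplementing*.
- In F3, F3.1, F3.2 and F5, state the same single primary outcome: the proportion of patients with at least one suicide attempt within 12 months of discharge.
- Name one deciding analysis. It can be the one-tailed Fisher test of F5. Or it can be the F3.2 odds ratio, with sidedness fixed and covariates listed in advance in place of selection by significance. The urn variables in D6 (gender, number of previous attempts, ideation versus attempt at intake) are an obvious list. If the odds ratio is chosen, restate power for it: .783 unadjusted with a two-sided 95% interval.
- Label total attempts and the ordinal GEE as supportive, and write down the ordinal categories before outcomes are compared by arm.
- If the team does want the ordinal measure to decide, define it, give its power, and change A1 and F5 to match.

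The cost is a few sentences and no new data. Stated power may fall below .82 if a two-sided analysis is chosen, and the supportive analyses can no longer settle A1.

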## **C. Preliminary Studies/Work Accomplished**

### **C1. Pilot Trial**

We have conducted a pilot clinical trial using identical subject selection and procedures to the trial proposed in this application. 86 patients who were admitted to a private psychiatric hospital due to a suicide attempt (n=35) or suicidal ideation with intent (N=51) received treatment as usual in the

community plus randomization to one of two treatment conditions: 1) SAFE or 2) CLASP for a six month period. Assessments were completed during hospitalization, and 3 + 6 months post discharge.

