**D. Research Design and Methods.**

## **D1. Overview**

Two hundred Veterans admitted to the Providence VAMC psychiatric inpatient unit or medical unit due to suicide attempt or suicidal ideation with any methods, plan, and/or intent to make an attempt will be recruited and randomly assigned to receive treatment as usual and either: a) SAFE or b) CLASP. The active interventions will begin during hospitalization and continue for 6 months post-discharge. After the intervention's end, patients will be followed for follow-up assessments for an additional 6 months (12 months post-discharge).

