### **D5. Assessments**

Participants will be assessed in-person at 5 time points: baseline, 3 months post-hospitalization, 6 months post-hospitalization, 9, and 12 months post-hospitalization. In addition to the usual demographic variables, we will assess seven areas: a) psychiatric diagnosis, b) suicidal ideation and behavior, c) hopelessness, d) social and family support, e) values, f) psychiatric symptoms, and g) treatment utilization. The specific measures to be used are listed in the following table. Detailed description of measures and their psychometric properties are limited to the references. Our assessment battery has been kept relatively brief in order to allow completion prior to hospital discharge and to enhance compliance at follow-up assessments.

We will make every effort to follow all subjects through the twelve-month period regardless of their continued participation in CLASP, SAFE or subsequent suicide attempts or hospitalizations. To reduce attrition, subjects will be paid \$50 in electronic funds transfer (EFT), cash, prepaid debit cards, or gift cards for completion of each follow-up assessment. If needed, we will conduct interviews by phone. Patients who are having continuing difficulties may feel discouraged and may fear that they have disappointed the experimenters. To encourage compliance among this group, patients will be

informed that the information they provide is extremely important regardless of how well they may feel they are doing.

	Baseline	3,6,9,12 month Follow-up
Demographics	X	
Diagnosis and Cognitive Impairment		
The McLean Screening Instrument for Borderline Personality Disorder (MSI-BPD) [49]	X	
Mini-Mental State Exam (MMSE) [50]	X	
Structured Clinical Interview for the DSM-IV Axis I Disorders (SCID-I) [51]	X	
Structured Clinical Interview for the DSM-IV Axis II Disorders – Borderline Personality Disorder (SCID-II BPD) [52]	X	
PTSD Checklist (PCL) [53]	X	X
Quick Inventory of Depressive Symptomology (QIDS) [54]	X	X
Psychiatric Diagnostic Screening Questionnaire (PDSQ) [55]	X	
Suicidal Ideation and Behavior		
Columbia Suicide Severity Rating Scale (C-SSRS) [48]	X	X
Longitudinal Interval Follow-Up Evaluation (LIFE) [56]– suicidal ideation and behavior		X
Record review (hospital, state death registry, national death registry)		X
Hopelessness		
Beck Hopelessness Scale [57]	X	X
Social and Family Support		
Social Support Behaviors Scale (SS-B) [58]	X	X
Values		

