### **F3.1 Operationalization of Outcomes.**

#### 1) Primary Outcome

- a. *Suicide Attempts*. The number of patients who make a subsequent suicide attempt and total number of attempts will be assessed using 12 month data collected from all possible sources, including follow-up assessments (C-SSRS), b) hospital chart reviews, c) significant other reports, and d) community clinician reports.

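### F3.2 plans an effect estimate for completed suicide, an outcome that item 3d expects to be too rare to analyse; with suicides in exactly one arm, a robust interval excludes 1 even at 0 vs 1 deaths

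*Combined protocol and SAP*

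**What the plan says.** Two statements about completed suicide stand close together in the analysis plan.

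- F3.1, Tertiary Outcomes, item d: because suicide is rare even in this population, "we do not expect to have sufficient numbers of patients who complete suicide for meaningful analyses". The number will be tracked from all available sources. The D5 table schedules those sources as "Record review (hospital, state death registry, national death registry").
- F3.2: after describing GEE "to estimate the ordinal response at each follow-up assessment", the plan says that similar analyses will give "estimates for the CLASP effect on the total number of attempts in each treatment condition, suicidal ideation, completed suicide", followed by re-hospitalization and treatment engagement. F3.2 also opens by promising an effect size for every outcome measure.

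The nearest antecedent of the similar analyses is GEE. The other candidate is the method given for the primary proportion, "using an odds ratio and its associated robust confidence interval". Section F has no rule for an arm without events. F1 says in general terms that data will be examined first and the estimation method chosen to suit them.

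**The concern.** Item 3d gives a sound reason not to model this outcome, and F3.2 then asks for a model of it. The mismatch matters because the method named behaves badly in the very situation that 3d foresees. With one or two deaths, all in the same arm, a GEE or logistic model with a robust variance does not return a wide, uninformative interval. It returns a narrow one, far from 1. An analyst who followed F3.2 literally could report an effect of CLASP on suicide death, in either direction, from a single patient. Readers would give great weight to such a statement about the gravest outcome in the trial.

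**Working it through.** **Inputs.**
- 200 patients (protocol introduction, D1). D2 gives 100 for CLASP, so 100 per arm is inferred.
- First-year suicide among attempters 0.8% to 2.6% (Background, B).
- Pilot: no suicides in 86 patients (C1.3), of whom 35 were "admitted to a private psychiatric hospital due to a suicide attempt (n=35") and 51 had ideation with intent (C1).
- A 95% level is assumed for the interval, since F3.2 states none. The sandwich variance is assumed for GEE: it is the usual choice and matches the robust interval named for the primary odds ratio, but the GEE sentence names no estimator.

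**The plan's own figure.** No power or precision is stated for completed suicide. The one figure that can be reproduced nearby is the power of .82 for suicide attempts in F5. A one-tailed Fisher test at 3/39 vs 10/47, 100 per arm and alpha .05 gives 0.833 by exact enumeration, within 2 points of .82. It does not bear on this outcome.

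**Why the robust interval fails.** Let the fitted risk in the empty arm be m, which tends to 0. Its log odds tend to minus infinity. Its sandwich variance is n·m²/(n·m)² = 1/n, which stays finite. The other arm, with proportion p, contributes 1/(n·p·(1−p)). So

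robust SE(log OR) = √[1/n + 1/(n·p·(1−p))].

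For 0/100 vs 1/100: √[0.01 + 1/(100 × 0.01 × 0.99)] = √(0.01 + 1.0101) = 1.010.

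A fitted binary GEE, one row per patient, agrees:

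| Deaths, CLASP vs SAFE | log OR | Robust SE | 95% interval for OR | Fisher two-sided p |
|---|---|---|---|---|
| 0 vs 1 | −20.97 | 1.010 | 1.1e-10 to 5.7e-9 | 1.00 |
| 1 vs 0 | +20.97 | 1.005 | 1.8e8 to 9.2e9 | 1.00 |
| 0 vs 2 | −21.67 | 0.721 | 9.4e-11 to 1.6e-9 | .50 |
| 0 vs 3 | −22.09 | 0.595 | 7.9e-11 to 8.2e-10 | .25 |

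The point estimate depends on where the software stops iterating, but the exclusion of 1 does not: a logistic fit halted after 6 iterations already gave 0.007 to 0.37. Four rows per patient give the same pattern (0 vs 1: SE 1.002, interval 2.2e-11 to 1.1e-9).

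**What valid methods give at 0 vs 1.** The exact conditional odds ratio is 0, with interval 0 to 39.0. Adding 0.5 to each cell gives 0.33 (0.013 to 8.2). Both intervals include 1. Fisher's two-sided p first falls below .05 at 0 vs 6 (p = .029; 0 vs 5 gives .059).

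**How often exactly one arm is empty.** Assume the same true rate r in both arms and let q = (1−r)^n be the chance that an arm has no suicide. Then P(exactly one empty) = 2q(1−q) and P(both empty) = q².

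| Assumption | r | q | Exactly one empty | Both empty |
|---|---|---|---|---|
| Rate applies to all, n = 100 | 0.8% | 0.448 | 49% | 20% |
| Rate applies to all, n = 100 | 2.6% | 0.072 | 13% | 0.5% |
| Only index attempters at risk, n = 41 (35/86 × 100) | 0.8% | 0.719 | 40% | 52% |
| Only index attempters at risk, n = 41 | 2.6% | 0.340 | 45% | 12% |

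In the first two rows the expected total is 200 × 0.008 = 1.6 to 200 × 0.026 = 5.2 deaths.

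**The case against.** **F1 allows judgement.** F1 requires the data to be examined and estimation to be fitted to their characteristics, and an empty arm is such a characteristic. This softens the point. It does not close it, because F1 names no exact, penalised or descriptive fallback and F3.2 still lists the outcome. F1 also adjusts interpretation for the number of tests, but a p value of about 1e-95, as at 0 vs 1, would survive any such adjustment.

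**Item 3d is a forecast, not a prohibition.** F3.2 could be read as the method to use if numbers allow. That is fair, but F3.2 does not state the condition.

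**The output may never appear.** Software may warn of separation or fail to converge, and a model-based variance would give an interval from 0 to infinity. A careful analyst would probably discard the result. This stands as a limit on the likely harm.

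**The rates are borrowed.** The 0.8% to 2.6% describes attempters. The trial also enrols patients with ideation only, and the pilot had 0 suicides in 86, so the true rate may be lower.

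**Stronger readings that a reader might infer.**
- That the interval misleads whenever an arm has no suicide. It does not: at 0 vs 0 it was 0.76 to 1.32, which is spuriously narrow but includes 1.
- That the treatment of visits after a death (missing, or carried as events) decides the result when both arms have deaths. The plan defines no visit-level suicide variable, and the effect needs extreme timings. With 1 vs 3 deaths all at the same visit, both codings give 0.328. Over all 256 timings of 1 vs 3, taken as equally likely, the codings disagree on excluding 1 in only 10 (3.9%).
- That the primary outcome is compromised because F3.1 does not say that a fatal attempt counts. The natural reading is that it does.

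**Conclusion.** The inconsistency is real and narrow. F3.2 prescribes an effect estimate for an outcome that 3d expects to be too rare to analyse. When exactly one arm has a suicide and the sandwich variance is used, the resulting 95% interval excludes 1 whatever the strength of the evidence, down to a single death. Under equal true rates, and with the background rate applied to all 200 patients, that configuration arises in 49% (at 0.8%) to 13% (at 2.6%) of trials. These are illustrations under a borrowed rate, not properties of this trial. The documents do not support a claim that the trial will report a false effect on suicide death; they support only that the text as written permits it and offers no safeguard specific to it. Completed suicide is a tertiary outcome. The primary analysis and the stated power of .82 are untouched. This is an inexpensive improvement, not a flaw in the design.

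**What to change.** In F3.2, delete completed suicide from the list of outcomes that receive an effect estimate, and exempt it from the opening promise of an effect size for every outcome. State instead that the number of suicides will be reported by arm with exact binomial intervals, descriptively, in line with 3d. For example, an arm with 0 of 100 would carry an upper 95% limit of 1 − 0.025^(1/100) = 3.6%.

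The cost is one deletion and one sentence, with no new data: the registry and record reviews are already scheduled in D5. The downside is that there will be no model-based effect estimate for suicide death, which the expected numbers could not support anyway.

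As an optional clarification, F3.1 could say that fatal attempts count in the primary event.
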